7.4.3 Concentrations adjusted for creatinine

Concentrations adjusted for creatinine in spot urine collection will be calculated as:

$$\text{Biomarker (adjusted for creatinine)} = \frac{[\text{Biomarker}]}{[\text{Creatinine}]}$$

where the [] indicated concentrations measured from the same spot urine collection.

This applies to NEQ, CEMA and total NNAL.

7.5 Tobacco and nicotine containing product dependence

7.5.1 ABOUT™ Dependence Questionnaire

Perceived dependence on tobacco and nicotine-containing products will be assessed via a subject self-reported outcome measure at V2 (Day -1), and at V6 using the ABOUT™-Dependence Questionnaire.

The value recorded at Day -1 will be considered the baseline value.

The questions or items to be answered by the subject in the ABOUT™ – Dependence Questionnaire are listed in Table 3.

Subjects will be asked to respond to the items in the questionnaire on a Likert type scale. For items 3a-3d, the response to and scoring of items are: 0 = “Not at all”; 1 = “A little”; 2 = “Moderately”; 3 = “Very much”; 4 = “Extremely”. For items 4a to 4j, the scoring of items are: 0 = “Never”; 1 = “Rarely”; 2 = “Sometimes”; 3 = “Most of the time”; 4= “All the time”.

For the purpose of deriving a score from ABOUT™-Dependence questionnaire for an individual, 3 multi-items domains will be considered: the behavioral impact domain (items 3a, 3b, 4a, 4c, 4e), the signs and symptoms domain (items 4b, 4d, 4f, 4g, 4h) and the extent of use domain (items 1 and 2). The raw score for each domain will be derived by adding the score of each individual items within the domain and a composite raw score obtained by adding the score of each of the 3 domains.

An overall maximum composite raw score of 50 can be derived from the instrument as follows: 10 from the ‘extent of use’ domain (the 6-point Likert-type scale produces a maximum raw score of 5 for each item [‘0’ more than 3 hours to ‘5’ 0 to 5 minutes]), and 20 for each of the other two domains (the 5-point Likert-type scale produces a maximum raw score of 4 for each item, [‘0’ not at all/never to ‘4’ extremely/all the time]).

The conversion tables below will then be used to derive the corresponding measure score which represents, for that individual, the level of perceived dependence associated with their tobacco and nicotine product (TNP) use. Table 4 provides the conversion for each domain for the transformation of participant raw score to the measure score ranging from 0 to 100 as measured separately by each of the extent of use, behavioral impact, and signs and symptoms domain.

Table 5 provides the conversion for the composite score from all three domains for the transformation of total raw score to the measure score ranging from 0 (no perceived dependence) to 100 (very high perceived dependence) as measured overall with the ABOUT™-Dependence questionnaire. There are also separate columns in the conversion table for the composite score based on TNP use types (e.g., multiple users of two or more TNPs), and different categories of exclusive TNP users. This takes into account the adjustment for differential item functioning by TNP user types and different categories of TNPs for the extent of use domain items in relation to the other two domains when computing the three domain composite raw score and measure score.

Note that scores cannot be accurately computed if there are missing responses for any item and no imputation of missing responses will be performed. (See Assessment of Behavioral Outcomes related to Tobacco and nicotine products. – Dependence - User Manual. First Edition. June 2019. PMPSA)

**Table 4: ABOUT™ - Dependence sum score to measure conversion By Domain**

Extent of Use Domain	Total raw score (complete data)	Measure score (transformed 0-to-100 scale)
0	0	0
1	17	
2	28	
3	36	
4	43	
5	50	
6	57	
7	64	
8	73	
9	85	
10	100	
Behavioral Impact Domain	Total raw score (complete data)	Measure score (transformed 0-to-100 scale)
0	0	0
1	14	
2	23	
3	29	
4	34	
5	38	
6	41	
7	44	
8	47	
9	50	
10	53	
11	56	
12	59	
13	62	
14	65	
15	69	
16	73	
17	77	
18	82	
19	90	
20	100	
Signs and Symptoms Domain	Total raw score (complete data)	Measure score (transformed 0-to-100 scale)
0	0	0
1	11	
2	19	
3	25	
4	30	
5	34	
6	37	
7	41	
8	44	
9	48	
10	51	
11	55	
12	58	

13	62
14	66
15	70
16	74
17	79
18	84
19	91
20	100

Table 5: ABOUT - Dependence sum score to measure conversion for the questionnaire composite score

Composite raw score (complete data)	Users of two or more TNPs Measure score (transformed 0-to-100 scale)	Exclusive users: P3P, HnB, Cigarettes, Smokeless tobacco, Pipe, NRTs Measure score (transformed 0-to-100 scale)	Exclusive users: e-Cigarettes Measure score (transformed 0-to-100 scale)	Exclusive users: Waterpipe, Cigars Measure score (transformed 0-to-100 scale)
0	0	0	0	0
1	15	16	13	16
2	22	22	20	23
3	26	27	25	28
4	30	30	29	31
5	32	32	31	34
6	35	35	34	36
7	37	36	36	38
8	38	38	38	40
9	40	40	39	42
10	42	41	41	43
11	43	43	42	45
12	44	44	44	46
13	46	45	45	47
14	47	47	46	48
15	48	48	47	49
16	49	49	48	50
17	50	50	49	51
18	51	51	50	52
19	52	52	51	53
20	53	53	52	54
21	54	54	53	54
22	55	55	54	55
23	56	55	54	56
24	57	56	55	57
25	58	57	56	57
26	58	58	57	58
27	59	59	58	59
28	60	59	58	59
29	60	60	59	60
30	61	61	60	61
31	62	61	61	61
32	62	62	61	62
33	63	63	62	63
34	64	63	63	63
35	64	64	63	64
36	65	65	64	65
37	66	65	65	65
38	66	66	65	66
39	67	67	66	67
40	68	68	67	67
41	69	68	68	68
42	70	69	69	69

43	71	70	69	70
44	72	71	71	71
45	73	73	72	73
46	75	75	73	74
47	77	77	75	77
48	81	80	78	80
49	87	86	83	87
50	100	100	100	100

The category of exclusive users at Day -1 are defined based on the tobacco and nicotine containing products use history/habits questionnaire:

- A subject will be a cigarette user if their average cigarette consumption over the last 3 months is greater or equal to 1 per day.
- A subject will be Pipe, or Smokeless tobacco, or NRTs user at Day -1 if Yes is answered to use of pipe, OR snuff or chewing tobacco OR NRT respectively among the tobacco/nicotine containing products listed in question 6 of the tobacco and nicotine containing products use history/habits for last 7 days
- A subject will be e-cigarette user at Day -1 if Yes is answered to use of e-cigarette among the tobacco/nicotine containing products listed in question 6 of the tobacco and nicotine containing products use history/habits for last 7 days
- A subject will be users of waterpipe at Day -1 if Yes is answered to use of Hookah among the tobacco/nicotine containing products listed in question 6 of the tobacco and nicotine containing products use history/habits for last 7 days

Exclusive user if Y in any category and N to others.

Exclusive users at end of study

At the end of the study, the flag will be based on **ALL** the e-diary data prior to Day 30:

- Subject will be Cigarettes or Smokeless tobacco or Pipe, or NRTs user at Day 30 if average use of any of the above $\geq 1/\text{day}$
- Subject will be e-cigarette user at Day 30 if average use of e-cigarette ≥ 1 per day
- Subject will be user of waterpipe or cigars at Day 30 if average use of pipe, cigars, or cigarillos ≥ 1 per day

7.6 CYP2A6

CYP2A6 activity is calculated in plasma as the metabolic ratio of trans-3' hydroxycotinine and cotinine, both expressed in molar equivalent (nmol/L):

$$CYP2A6 = \frac{HCOT[\text{ng/mL}] \times 5.202}{COT[\text{ng/mL}] \times 5.675}.$$

Any values below the LLOQ or above the upper limit of quantification (ULOQ) in the component parameters will not be imputed and the derived variable will be set to missing.

The conversion factor will be applied as follows:

Cotinine (COT)	The molecular weight is 176.2178 g/mol. Therefore to transform COT from ng/mL to nmol/L, the result in ng/mL will be multiplied by 5.675.
Trans- 3'hydroxycotine (HCOT)	The molecular weight is 192.217 g/mol. Therefore to transform HCOT from ng/mL to nmol/L, the result in ng/mL is multiplied by 5.202.

The converted results will be reported to three decimal places and the ratio will be reported as a percentage.

Value obtained at Day 1 prior to any product use will be considered the baseline value.

7.7 Weighing of P3P Products

At Day 1 and Day 30, P3P used for PK assessment should be weighed before product use and as early as possible (but within maximum 1 hour) after the end of product use. Weight difference (before – after product use) will be calculated.

7.8 Safety Variables

7.8.1 ECG

The QT interval corrected using Fridericia's formula (QTcF) will be calculated as follows:

$$QTcF = \frac{QT}{\sqrt[3]{(60/HR)}}$$

The QT interval corrected using Bazett's formula (QTcB) will be calculated as follows:

$$QTcB = \frac{QT}{\sqrt[2]{\left(\frac{60}{HR} \right)}}$$

7.8.2 Cough Assessment

At V2-V6, subjects will be asked if they have experienced a regular need to cough, e.g., whether they have coughed several times in the previous 24 hours prior to assessment. If the answer is 'yes', they will be asked to complete a cough assessment questionnaire (which includes a VAS and three Likert scales).

The VAS will assess how bothersome cough is to the subject, on a 10 cm scale ranging from 'not bothering me at all' to 'extremely bothersome'.

Subjects will also be asked to assess the intensity and frequency of cough and the amount of sputum production on Likert scales as presented in Table 6: Cough Assessment Likert Scales.

Table 6: Cough Assessment Likert Scales

Question	Likert Scale
1 The intensity of cough	1 = very mild 2 = mild 3 = moderate 4 = severe 5 = very severe
2 The frequency of cough	1 = rarely 2 = sometimes 3 = fairly often 4 = often 5 = almost always
3 The amount of sputum production	0 = no sputum 1 = a moderate amount of sputum; 2 = a larger amount of sputum; 3 = a very large amount of sputum.

7.9 Categorical Variables

The categorical variables used in this study are shown below (Table 7).

**Table 7: Categorical Variables Definitions Other Than Reported in eCRF**

Variable	Categories
Demographics	
BMI (kg/m ²)	Underweight: < 18.5 Normal range: ≥ 18.5 and < 25.0 Overweight: ≥ 25.0 and < 30.0 Obese: ≥ 30.0
Product Exposure Categories	≤ 5 P3P-1mg /Day $>5-10$ P3P-1mg /Day >10 P3P-1mg /Day ≤ 5 P3P-2mg /Day $>5-10$ P3P-2mg /Day >10 P3P-2mg /Day
Product Exposure Periods	
Detailed Product Exposure Periods	Product test Day 1 Day 2 Period 1 ([D3 –V3]) Period 2 ((V3-V4]) Period 3 ((V4-V5]) Period 4 ((V5-V6])
Overall exposure period	Day 1 to Day 29 inclusive

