### 6.2.2 Product use during confinement (V2, V6)

During the investigational period subjects will be requested to attend two on-site visits with overnight stays (with a confinement of 3-days at V2 and 2-days at V6). At the beginning of these visits, subjects will be asked to give their cigarettes and used/unused P3P products to the site staff.

Smoking cigarettes and/or use any tobacco/nicotine containing products other than P3P will not be allowed on site during the visits. On the first day of V6 (Day 29), subjects will be allowed to use P3P until the evening which will be subsequently followed by a wash-out period of at least 10 hours prior to the PK assessments which will be done on the second day of the visits. P3P use on the first day of V2 will only be allowed during the product test period (section [6.2.1](#)). P3P will be dispensed by the site staff on a product by product basis during the timeframe allowed by the protocol. The distribution should be recorded at site logs by site staff and the use of any product during the confinement days should be also recorded in the product use diary which is completed by the subject. The time of the use of the last tobacco/nicotine containing product, prior to the start of the wash-out period should be recorded.

In the morning of the second day of V2 (Day 1) and V6 (Day 30), following at least 10 hours of abstinence from any tobacco and nicotine containing products, subjects will use a single P3P product with no restrictions on the number of puffs or puffing frequency (*ad libitum* use) for a duration of up to 15 minutes. The start of product use (first puff) will be considered as  $T_0$ . The start and stop time of product use will be recorded. At V2 (Day 1), after the end of the blood sampling for PK assessments (4h after  $T_0$ ) subjects will be allowed to restart the use of

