#### Confidentiality Statement

Data and information contained in this document are considered to constitute trade secrets and confidential commercial information, and the legal protections provided to such trade secrets and confidential information are hereby claimed under the provisions of applicable law. No part of this document may be publicly disclosed without the written consent of Philip Morris Products S.A.

P3P. Subjects will remain on-site until the evening of Day 2 and will be allowed to use up to 15 P3P products/day on Day 1 and Day 2. During this time, subjects will not be allowed to smoke cigarettes and/or use any other tobacco/nicotine containing products with the exception of P3P.

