#### 6.2.3 Ambulatory Exposure Period (Discharge at V2 until start of V6)

Subjects will be instructed to use P3P exclusively (using up to 15 products daily) from discharge at V2 until check-in at V6. Use of cigarettes and/or other tobacco and nicotine containing products during the ambulatory Exposure Period will not be a reason for discontinuing a subject from the study, but should be avoided as much as possible. During the entire exposure period, subjects will report their daily consumption in a product use diary (section 7.8.1)

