7.3.3 Nicotine/tobacco product use

Subjects will enter the number of P3P consumables used per day, the number of cigarettes used per day, or/and other tobacco and nicotine containing products used per day in a product use diary from Day 1 until the Discharge at V6 (including during the visits). For subjects who decide to quit using all tobacco and nicotine containing products the product use will no longer be captured. See section 7.9 for the definition of product exposure periods.

Average P3P consumables used per day during a period = Total number of P3P consumables used during the period/ duration of the period.

Similar definition will be made for:

- Average Cigarettes smoked per day during a period
- Average Heat not burn and/or smokeless tobacco products used per day during a period
- Average Other tobacco products (pipe, cigar, cigarillos, chewable...) used per day during a period
- Average occasions Electronic Cigarette used per day during a period

Also, the percentage of subjects having used any Nicotine Replacement Therapies over the period will be provided.

Change from baseline in average number of cigarettes used per day = Average number of cigarettes used per day reported at Screening - Average number of cigarettes used per day per period.

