12.5.4 Nicotine/Tobacco product use

The following variables:

- Average Cigarettes smoked per day during a period
- Change from baseline in average number of cigarettes used per day during a period

- Average Heat not burn and/or smokeless tobacco products used per day during a period
- Average Other tobacco products (pipe, cigar, cigarillos, chewable...) used per day during a period
- Average occasions Electronic Cigarette used per day during a period
- Percentage (%) of P3P used during a period with % P3P = $100 * \text{number of P3P} / (\text{number of P3P and CC})$
- Percentage of subjects having used any Nicotine Replacement Therapies during a period

will be summarized in a descriptive manner for each period being the time interval between 2 consecutive visits and also for the complete exposure period.

The data will be presented in the below outputs:

TFL number	Title
TABLES	
15.2.18.1	Descriptive Statistics of Average Cigarettes smoked /day - By Period – Safety Population
15.2.18.2	Descriptive Statistics of Average Cigarettes smoked /day By Product Exposure Category (≤ 5 P3P/day, $> 5 - 10$ P3P/day, > 10 P3P/day) - By Period – Safety Population
15.2.18.3	Descriptive Statistics of Change from Baseline in Average Cigarettes smoked /day - By Period – Safety Population
15.2.18.4	Descriptive Statistics of Average Heat not burn and/or smokeless tobacco products used /day - By Period – Safety Population
15.2.18.5	Descriptive Statistics of Average Other tobacco products (pipe, cigar, cigarillos, chewable...) used/day - By Period – Safety Population
15.2.18.6	Descriptive Statistics of Average occasions Electronic Cigarette used /day - By Period – Safety Population
15.2.18.7	Descriptive Statistics of Percentage (%) of P3P use - By Period – Safety Population
15.2.18.8	Percentage of subjects having used any Nicotine Replacement Therapies – By Period
LISTINGS	
15.1.18.1	Listing of Nicotine/Tobacco product use - By Period

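### The overall Day 1 to Day 29 summaries of cigarettes per day and P3P share include days when smoking is banned, which slightly overstates the within-group switch

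*SAP*

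**What the plan says.** SAP 7.3.3 defines average use as "Total number of P3P consumables used during the period/ duration of the period" and gives cigarettes and the other products a similar definition. For the periods it directs the reader elsewhere: "See section 7.9 for the definition of product exposure periods". There, Table 7 gives the overall exposure period as "Day 1 to Day 29 inclusive". It also lists Day 1 and Day 2 as periods of their own, starts Period 1 at Day 3, and closes Period 4, (V5-V6], on the V6 day.

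SAP 12.5.4 summarises cigarettes per day, change from Screening and P3P as a percentage of P3P plus cigarettes for "each period being the time interval between 2 consecutive visits and also for the complete exposure period". The change is the Screening average minus the period average, so a positive value is a reduction. Diary entries run "from Day 1 until the Discharge at V6 (including during the visits".

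Protocol 6.2.2 sets the restrictions. For the V2 stay, which ends on the evening of Day 2, "subjects will not be allowed to smoke cigarettes and/or use any other tobacco/nicotine containing products with the exception of P3P". For both confinement visits, "Smoking cigarettes and/or use any tobacco/nicotine containing products other than P3P will not be allowed on site during the visits". V6 begins on Day 29, when subjects hand in their cigarettes.

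**The concern.** Secondary objective 3 looks at how far subjects move from cigarettes to P3P, and the reference is what they reported smoking in ordinary life over the three months before Screening. The overall average mixes days on which the subject chose with days on which the protocol chose. On the latter, cigarettes are zero and P3P is the only permitted product, whatever the subject would have done.

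The effect runs one way: it lowers cigarettes per day and raises the P3P share. Change in cigarettes per day is a topline output (Table 15.2.18.3, SAP 13.2). A reader who takes its overall row as the measure of switching would credit the product with a reduction that the confinement imposed.

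**Working it through.** The plan states no figure to reproduce. Sample size is empirical and these endpoints are descriptive. The check is arithmetic on the SAP's own definitions.

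**Inputs**
- D = 29 days (SAP Table 7).
- b = Screening rate, 5 to 15 cigarettes per day (Protocol 5.1.1).
- k = smoke-free days created by the ban. Day 1 is wholly confined. Day 2 is confined until discharge after 6:30 PM (Protocol Table 8). Day 29 is confined from check-in, whose time is not given. So k = 2 means Days 1 and 2 in full, and k = 3 adds all of Day 29. Both are upper bounds. k = 1 (Day 1 only) is the floor, reached if a subject smokes the full daily number after discharge on Day 2 and before check-in on Day 29.
- c = cigarettes per day when free to smoke, taken as unaffected by the ban (assumption).

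**Cigarettes per day**

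Overall average = c(D − k)/D. Reported reduction = b − c(D − k)/D. For a subject who does not switch, c = b and the reduction is bk/D:

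| | k = 1 | k = 2 | k = 3 |
|---|---|---|---|
| Share of window, k/29 | 3.4% | 6.9% | 10.3% |
| b = 5 | 0.17 | 0.34 | 0.52 |
| b = 10 | 0.34 | 0.69 | 1.03 |
| b = 15 | 0.52 | 1.03 | 1.55 |

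If the window is taken to end at the actual V6 day (Day 27 to 31, from the visit window of 2 days either side), two days make up 6.5 to 7.4% of it and three days 9.7 to 11.1%.

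For subjects who do switch, at b = 10:

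| True reduction | Overall average, k = 2 and 3 | Reported reduction |
|---|---|---|
| 20% (c = 8) | 7.45 and 7.17 | 25.5% and 28.3% |
| 50% (c = 5) | 4.66 and 4.48 | 53.4% and 55.2% |
| 90% (c = 1) | 0.93 and 0.90 | 90.7% and 91.0% |

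**P3P share**

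With p P3P per day when free and q when confined, the overall share is 100[p(D − k) + qk]/[(p + c)(D − k) + qk]. The documents give no expected p or q, only a cap of 15 per day, so the values below are assumptions. With p = c = 5 (true share 50%), for k = 2 and 3:
- q = 5: 51.8% and 52.7%
- q = 10: 155/290 = 53.4% and 160/290 = 55.2%
- q = 15: 165/300 = 55.0% and 175/305 = 57.4%

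**Period 4**

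At nominal timing it covers Days 23 to 29, seven days. The V6 day removes at most 1/7 = 14.3%, or 0.5/7 = 7.1% if half of it is spent on site.

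**Ambulatory days only**

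Day 3 to Day 28 is 26 days. The average is then c, the non-switcher's reduction is 0, and the share is p/(p + c), which is 50% in the example. Only the on-site hours at V3 to V5 remain.

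**The case against.** Much of the difficulty is already visible in the plan. Table 7 separates Day 1 and Day 2, Periods 1 to 3 contain no overnight confinement, and Table 15.2.18.3 is produced by period, so largely ambulatory figures stand beside the overall one. The wide window also follows the endpoint: objective 3 asks for product use over Day 1 to Day 30 and for change in cigarettes across the whole study. The Day 1 to 29 average is a true description of consumption over those days. The percentages are upper bounds, and the worst case is a subject who does not switch, although entry requires readiness to do so. The study is descriptive, and SAP 12.5.4 plans no test of these variables.

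All of that stands, and it limits the point to interpretation and labelling of the overall row and Period 4. It does not remove the point. No pooled ambulatory figure is planned, the overall row does not show that it contains banned days, and the last period, where adaptation would be read, includes the V6 day.

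A reader might go further and infer that the 1 mg versus 2 mg comparison is biased. The documents do not support that: the same ban applies to both arms, and average cigarettes per day is scaled by the same factor, 27/29 to 26/29, in each.

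**Conclusion.** The point holds, at modest size, for the overall Day 1 to 29 row and for Period 4. For a subject who smokes at the Screening rate whenever free, the overall average is understated by up to about 7% (Days 1 and 2) to 10% (adding a full Day 29), at most 0.34 to 1.55 cigarettes per day across the eligible range. The relative distortion is largest for those who barely switch and negligible for near-complete switchers. It rests on whole-day abstinence on the counted days and on an unchanged rate when free. The effect on P3P share also depends on assumed use levels.

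Two stronger readings should be resisted. One is that the reported switch is mainly a product of confinement: at 10 cigarettes per day, a true 50% reduction moves by 3.4 to 5.2 percentage points at most. The other is that the Day 1 to 29 window is an error to be deleted. It follows the protocol's endpoint and is the basis of the product exposure categories (SAP 12.1.7), which are used in the Randomized and PK populations as well as in safety (SAP 12.1.1).

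**What to change.** In SAP Table 7:
- Add an overall ambulatory period, from Day 3 to the day before V6 check-in. This matches the free-use window that Protocol 6.2.3 already names in its heading, counted in whole days.
- End Period 4 on the day before V6 check-in (Days 23 to 28 at nominal timing) and show the V6 day separately.
- Keep Day 1 to 29 as the protocol-endpoint summary and as the basis of the exposure categories, labelled as including confinement days.

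In the 15.2.18.x tables, including topline 15.2.18.3, report cigarettes, other products, change from Screening and P3P share for the new period, and base any statement about switching on it.

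Reconcile the diary start as well. SAP 7.3.3 starts it on Day 1, while footnote o of the schedule of events starts it at check-out of Day 1, although subjects stay on site until the evening of Day 2. This decides whether Day 1 is counted.

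The cost is one extra row per table, a small programming change, and an overall reduction that reads slightly less favourably. Table 15.2.18.2 would set ambulatory cigarette figures against exposure categories defined on Day 1 to 29, so it needs a footnote.
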